**How does dysphagia assessment in acute stroke affect pneumonia?**

**Statistical Analysis Plan**

## Statistical Analysis Plan

### Research background

Stroke-associated pneumonia (SAP) is a common post stroke infection affecting 14% of patients (Kishore et al. 2015) and is associated with an increased risk of hospital mortality (Westendorp et al. 2011) and prolonged hospital stay (Finlayson et al. 2011). The combination of stroke-induced immune-deficiency and aspiration of oropharyngeal secretions and gastric contents into the lungs secondary to impaired consciousness and dysphagia predisposes patients to SAP in the first few days post stroke (Hannawi et al. 2013). Patients with dysphagia with confirmed aspiration have an 11-fold increased risk to SAP (Martino et al. 2005). However, up to half of patients with SAP do not aspirate (Westendorp et al.), which reflects SAP's multifactorial pathophysiology.

There is wide variation in the assessment and management of dysphagia in acute phase stroke and there is the potential for a range of medical interventions and clinical processes to be associated with risk of SAP (Eltringham et al. 2018, 2019). This research aims to find out how methods of dysphagia assessment and clinical management during the first 72 hours of admission to hospital affect the risk of stroke patients developing SAP and what care processes and interventions specific to patients with dysphagia affect the risk of stroke patients developing SAP during acute phase stroke.

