### **Sampling plan**

Hospital teams were included if they were registered on the SSNAP register for October-December 2019 and had sufficient records/data to report and were an active Hyper/Acute Stroke Unit. One hundred and sixty-six hospital teams were included after exclusions. The SLT Clinical Lead for Acute Stroke or the most appropriate person was identified in each team to complete the survey on behalf of their Stroke Unit. A distribution list with their name and email address was created.

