## **Statistical analyses**

Only completed surveys will be analysed. The survey data will be analysed using descriptive and inferential statistics. Descriptive statistics will include analysis of categorical and continuous data. Descriptive statistics of categorical variables will be frequency analysis i.e., percentage of the different categories within each variable. For example, proportion of Hospital Teams that are Routinely Admitting Teams and Non-Routinely Admitting Acute Teams. Categorical data will be visualised with bar and pie charts. The evaluation method for continuous data (incidence of pneumonia) will be mean and standard deviation to evaluate the dispersion of pneumonia incidence across the hospital teams and visualised using histograms.

Inferential statistics (linear regression analysis) will be used to test the hypotheses and explore if there is an association between the dependent variable (incidence of stroke-associated pneumonia) and independent binary variables: 1. Hospital Teams that use Water only dysphagia screening protocols (DSP) versus Hospital Teams that use water and other consistencies DSPs, 2. Hospital teams that use written guidelines for the first specialist clinical bedside swallow assessment versus Hospital teams that do not use written guidelines for the first specialist swallow assessment, 3. Hospital Teams that insert Nasogastric Tubes (NGTs) overnight have increased risk of SAP compared to Hospital Teams that do not insert NGTs overnight and 4. Hospital Teams with a written oral care protocol versus those do not have a written oral care protocol. Linear regression analysis will be visualised using Model Summary tables with Coefficients and 95% Confidence Intervals.

The proposed analysis for each variable is given in Table 1.

Table 1 – Proposed analysis for each variable

Variable	Data Source (s)	Values	Type of variable	Analysis approach	Methods for summarising data
Hospital Team	Survey Question #3 Please type the name of your hospital and select from the drop-down menu. SSNAP 2019 Team Centred 72-hour cohort data	1 = Routinely Admitting Team 2 = Non-Routinely Admitting Team	Categorical – Nominal - dichotomous	Descriptive statistics (frequencies) - Proportion of completed surveys for Routinely Admitting Team and Non-Routinely Admitting Acute Teams by SCN Region	Table

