## Method for analysing the data for incidence of stroke-associated pneumonia

Stroke-associated pneumonia (SAP) will be defined as the administration of antibiotics for a new clinical diagnosis of pneumonia in the first 7 days after admission as determined by the treating physician. SSNAP Patient Centred Post 72-hour quarterly data for Antibiotics for newly acquired pneumonia in the first 7 days from clock start will be used to calculate an annual 2019 pneumonia percentage for each team to measure the dispersion of the of pneumonia incidence across the teams.

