## **Sensitivity analysis**

Sensitivity analysis will be undertaken to understand how certain values contribute to the overall uncertainty of the model. For example, the impact of a lower-than-average response rate from a particular SCN region or the latest SSNAP annual data which includes data for the Covid-19 period compared to 2019 data (pre Covid-19).

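### No H1–H4 regression includes SCN region, so any regional pattern shared by practice and pneumonia would go unadjusted; a region fixed-effects version beside each planned model is worth considering

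*SAP*

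**What the plan says.** The outcome is a team-level figure. SSNAP quarterly data "will be used to calculate an annual 2019 pneumonia percentage for each team" (SAP, Method for analysing the data for incidence of stroke-associated pneumonia). The survey population is a census: "One hundred and sixty-six hospital teams were included after exclusions" (Sampling plan). Only completed surveys are analysed.

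The inferential plan is linear regression to "explore if there is an association between the dependent variable (incidence of stroke-associated pneumonia) and independent binary variables" (Statistical analyses). The Table 1 rows for survey questions 9, 20, 37 and 39 each name the pneumonia outcome and one binary practice variable. They name no region term, other covariate, random effect, or clustered or robust standard error. The output is fixed as well: "Linear regression analysis will be visualised using Model Summary tables with Coefficients and 95% Confidence Intervals".

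SCN region appears twice. In the Hospital Team row of Table 1 it splits a description of response: "Proportion of completed surveys for Routinely Admitting Team and Non-Routinely Admitting Acute Teams by SCN Region". Under Sensitivity analysis it is one of two examples: "the impact of a lower-than-average response rate from a particular SCN region". The purpose given there is general, "Sensitivity analysis will be undertaken to understand how certain values contribute to the overall uncertainty of the model", and no method follows. The SAP does not give the number of SCN regions.

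**The concern.** The exposures are written protocols and service policies, which neighbouring services can share. The outcome is antibiotic treatment for pneumonia as judged by the treating physician, so local habits of diagnosis and prescribing can affect it. Two separate problems could follow.

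- **Intervals too narrow.** If both the practice variable and the outcome cluster by region, residuals correlate within region and ordinary least squares understates the standard error. Both must cluster; one alone does no harm.
- **Confounding.** If regions that favour a practice also tend to record more, or less, pneumonia, the coefficient mixes the regional difference with the practice difference.

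The coefficient and its interval are the whole inferential result of an observational comparison, and nothing planned would reveal either problem. The sensitivity example does not fill the gap: it concerns who responded, and full response from every region would leave both problems in place.

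**Working it through.** The SAP states no effect size, SD, ICC, power or number of regions, so there is no figure of its own to reproduce.

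**Inputs.** From the SAP: at most 166 teams, one pneumonia percentage per team, binary exposures, 95% intervals. Assumed: 10 to 20 regions, 83 to 166 responding teams, ICCs from 0 to 0.3, exposure split 50:50.

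**Step 1: interval width.** With m teams per region, the variance of the slope is inflated by 1 + (m − 1) × ICC_practice × ICC_pneumonia, where ICC_practice is on the binary scale. The true standard error is the square root of this times the naive one. Over 83 to 166 teams and 10 to 20 regions:

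| Both ICCs | True SE / naive SE |
|---|---|
| either is 0 | 1.00 |
| 0.1 | 1.02 to 1.08 |
| 0.2 | 1.06 to 1.27 |
| 0.3 | 1.13 to 1.55 |

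**Step 2: false-positive rate with 14 assumed regions.** Here the practice ICC refers to an underlying normal variable cut at its median. Its binary-scale value is (2/π) × arcsin(ICC): 0.1 becomes 0.064 and 0.3 becomes 0.194.

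- 166 teams, m = 166/14 = 11.86, both ICCs 0.1: 1 + 10.86 × 0.064 × 0.1 = 1.07. SE ratio 1.034; rate 2 × [1 − Φ(1.96/1.034)] = 5.8%. Simulation: 5.7%.
- 166 teams, pneumonia 0.2, practice 0.3: 1 + 10.86 × 0.194 × 0.2 = 1.42. SE ratio 1.19; rate 10.0%. Simulation: 9.8%.
- 83 teams, m = 5.93, same ICCs: 1 + 4.93 × 0.194 × 0.2 = 1.19. SE ratio 1.09; rate about 7.2%. Simulation: 7.3%.

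**Step 3: confounding.** Let regional practice and regional pneumonia correlate at 0.5, with no true effect of practice. Teams on either side of the median cut differ by 2 × √(2/π) = 1.596 SD on the underlying practice variable. The large-sample bias in outcome SD is 0.5 × √(ICC_practice × ICC_pneumonia) × 1.596.

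- Both ICCs 0.1: 0.5 × 0.1 × 1.596 = 0.080.
- Both ICCs 0.2: 0.5 × 0.2 × 1.596 = 0.160.

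Simulation with 166 teams and 15 assumed regions (4,000 runs) gave:

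| ICCs (both) | Regional correlation | Bias, SD | Coverage, planned model | Coverage, region fixed effects |
|---|---|---|---|---|
| 0.1 | 0 | 0.00 | 94.6% | 95.3% |
| 0.2 | 0 | 0.00 | 92.5% | 95.3% |
| 0.3 | 0 | 0.00 | 87.8% | 95.0% |
| 0.1 | 0.5 | 0.08 | 91.4% | 95.3% |
| 0.2 | 0.5 | 0.15 | 81.6% | 94.9% |

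**Step 4: which adjustment.** A random intercept assumes region effects are unrelated to practice, which is what confounding violates. With correlation 0.5, 166 teams and 14 regions, a random intercept with known variance components left 0.034 of a bias of 0.072 SD (ICCs 0.1), or 47%. It left 0.043 of 0.153 SD (ICCs 0.2), or 28%. Region fixed effects removed the bias.

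**Step 5: cost if region is irrelevant.** Fixed effects multiply the standard error by about √[(N − 1)/(N − G)], where N is the number of teams and G the number of regions. With 14 regions this is √(165/152) = 1.04 for 166 teams and √(82/69) = 1.09 for 83. Simulation gave about 4% and 8%.

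**The case against.** The strongest reply is that nothing in the SAP ties practice or pneumonia to region. The background says "There is wide variation in the assessment and management of dysphagia in acute phase stroke" without attributing that variation to region. The rationale for Hypothesis 1 speaks of local screening protocols, and survey question 5 asks whether the hospital developed its own screen, so the variation may lie between hospitals rather than regions. Every ICC and the number of regions in the working is assumed. At low ICCs or with few responders the effect almost vanishes. All of this stands, and it limits the point to a conditional risk.

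Three stronger readings are tempting, and the SAP supports none of them.

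- *Region is used only to describe response.* The Sensitivity analysis section also names it in relation to the model's uncertainty, although the example is about uneven response.
- *The plan accepts that region affects the result.* Both mentions concern who responded, not regional patterns in care or pneumonia.
- *The H1–H4 estimates are regionally confounded.* No statement in the SAP shows this. Even that region is recorded for every team is an inference from the planned response table.

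It is also fair to say that region is one part of a wider gap. The regressions name no covariate, not even team type. The Missing data methodology section also allows one respondent's answers to stand for two teams, which is a closer source of dependence than region. Adjusting for region does not settle those matters.

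**Conclusion.** The point holds as a conditional one. The SAP names region twice but no H1–H4 model includes it, and the uneven-response example handles neither within-region correlation nor regional confounding. Harm to the intervals needs both practice and pneumonia to cluster by region; bias needs the two regional patterns to be correlated as well.

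From clustering alone, the false-positive rate runs from about 5.7% (both ICCs 0.1) to about 10% (0.2 for pneumonia, 0.3 for practice) with all 166 teams responding and 14 assumed regions. With 83 responders the second figure falls to about 7%. Confounding at a regional correlation of 0.5 is the more serious case, with bias of about 0.08 to 0.15 outcome SD and coverage of about 91% to 82% at ICCs of 0.1 to 0.2 (15 assumed regions). The documents cannot show which of these cases applies. Priority: consider.

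**What to change.** Under Sensitivity analysis, name a region-adjusted version of each H1–H4 model: the same linear regression with SCN region as fixed effects, giving a within-region estimate. Report it beside the planned unadjusted coefficient and 95% interval, and state the number of regions and of responding teams in each. A random-intercept model may be added, but should not be relied on to remove confounding.

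The cost is one degree of freedom per region beyond the first. If region does not matter, the adjusted interval is about 4% wider with 166 teams and 8% to 9% wider with 83. If practice itself clusters strongly, the loss is larger, because regions where every responding team gives the same answer contribute nothing to the within-region estimate. For that reason the adjusted result should accompany the planned one, not replace it. No new data are needed if region is recorded for every responding team, as the planned response table implies.

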## Data sets

Data from the Sentinel Stroke National Audit Programme registry will be used ([www.strokeaudit.org](http://www.strokeaudit.org)). Data will include administration of antibiotics for a new clinical diagnosis of pneumonia in the first 7 days after admission (Patient Centred Post 72-hour data) and Key indicators 4.5 Percentage of applicable patients who were given a swallow screen within 4h of clock start and 4.6 Percentage of applicable patients who were given a formal swallow assessment within 72h of clock start (Team Centred results). 2019 quarterly data will be used to create an annual 2019 data set.

## Method for analysing the data for incidence of stroke-associated pneumonia

Stroke-associated pneumonia (SAP) will be defined as the administration of antibiotics for a new clinical diagnosis of pneumonia in the first 7 days after admission as determined by the treating physician. SSNAP Patient Centred Post 72-hour quarterly data for Antibiotics for newly acquired pneumonia in the first 7 days from clock start will be used to calculate an annual 2019 pneumonia percentage for each team to measure the dispersion of the of pneumonia incidence across the teams.

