## **Overview of Study design**

A mixed mode survey design comprising of a self-administered electronic survey with a secondary option of a postal survey. The sample frame was

Routinely Admitting, and Non-Routinely Admitting Acute Stroke Hospital Teams registered on the Sentinel Stroke National Audit Programme (SSNAP) register. The survey population was Speech and Language Therapy (SLT) Clinical Leads for Acute Stroke in Hyper/Acute Hospital Stroke Units in England and Wales. The total survey population were surveyed. Survey participants were asked to respond about practice on behalf of the Stroke Unit rather than as an individual practitioner.

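### Non-Routinely Admitting Teams' own screening answers may not be the exposure their patients received, mainly in Hypothesis 1; a Routinely Admitting Teams-only regression should be prespecified beside the all-team one

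*SAP*

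**What the plan says.** The sample frame in *Overview of Study design* is "Routinely Admitting, and Non-Routinely Admitting Acute Stroke Hospital Teams registered on the Sentinel Stroke National Audit Programme (SSNAP) register", and *Sampling plan* reports that "One hundred and sixty-six hospital teams were included after exclusions". The split between RATs and N-RATs is not given.

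The exposures come from the survey: "Survey participants were asked to respond about practice on behalf of the Stroke Unit rather than as an individual practitioner". Table 1 uses Q9 (water-only screening protocol) as the predictor for Hypothesis 1 and Q20 (written guidelines for the bedside assessment) for Hypothesis 2.

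For the outcome, *Method for analysing the data for incidence of stroke-associated pneumonia* will "calculate an annual 2019 pneumonia percentage for each team". It describes the window in two ways: "antibiotics for a new clinical diagnosis of pneumonia in the first 7 days after admission as determined by the treating physician" in the definition, and "Antibiotics for newly acquired pneumonia in the first 7 days from clock start" for the data item actually used.

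*Data sets* lists the registry indicator "Percentage of applicable patients who were given a swallow screen within 4h of clock start" and a companion indicator for formal assessment within 72 hours of the same clock. *Research background* says that the mechanism "predisposes patients to SAP in the first few days post stroke".

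Team type is coded in the Hospital Team row of Table 1, but only for descriptive frequencies. It is not a covariate, stratum or restriction in the regressions, and the examples under *Sensitivity analysis* (regional response rate, Covid-period data) do not include it. *Missing data methodology* allows one survey to stand for a RAT and an N-RAT in the same Trust if the respondent confirms that practice is the same.

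**The concern.** Hypothesis 1 concerns a step that the cited indicator times within hours of clock start, and the pneumonia window opens at that same moment. A team labelled as not routinely admitting will often take over a patient after that step. Its Q9 answer then describes its own protocol, while the screen its patients received, and part of the 7-day risk period, belonged to another unit. Pairing that answer with pneumonia counted from clock start is misclassification of exposure.

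This differs from N-RATs simply having higher or lower pneumonia rates. A team-type term in the model absorbs a difference in level, but the wrong exposure value stays in those rows.

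At stake is how an all-team result for Hypothesis 1 is read. That hypothesis is stated as a null, so a coefficient near zero could be reported as no difference between protocols when part of the explanation is whose protocol was recorded.

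**Working it through.** The plan states no sample size, effect size, standard deviation or N-RAT share, so there is no figure to reproduce. What follows is illustration on assumed inputs.

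**1. Shrinkage with equal exposure mix.** Let f be the N-RAT share of analysed teams, and k the share of N-RATs whose answer matches the admitting team's practice, the rest being unrelated to it. Let exposure prevalence p be the same in both team types, and let the outcome depend on the admitting team's practice with true slope β. Only RAT rows and matching N-RAT rows contribute covariance:

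- covariance = [(1 − f) + f·k]·p(1 − p)·β
- variance of the recorded exposure = p(1 − p)
- pooled slope = β·[1 − f(1 − k)]

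| f | k = 0 | k = 0.5 | k = 1 |
|---|---|---|---|
| 5% | 0.95β | 0.975β | β |
| 10% | 0.90β | 0.95β | β |
| 20% | 0.80β | 0.90β | β |
| 30% | 0.70β | 0.85β | β |

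Simulation agreed: with β = 2 and f = 20%, the pooled slope was 1.6 at k = 0 and 1.8 at k = 0.5. If only some of an N-RAT's patients were screened elsewhere, the shrinkage is smaller.

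**2. Direction when team types differ.** Take β = 2, f = 20%, k = 0, exposure prevalence 50% in RATs and 80% in N-RATs, and N-RAT pneumonia 3 points higher or lower.

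- Overall prevalence: 0.8 × 0.5 + 0.2 × 0.8 = 0.56; variance 0.56 × 0.44 = 0.2464
- Covariance within RATs: 0.8 × 0.25 × 2 = 0.400; within N-RATs: 0
- Covariance between types: 0.8 × 0.2 × 0.3 × (±3) = ±0.144
- Pooled slope: 0.544 / 0.2464 = 2.21, or 0.256 / 0.2464 = 1.04 (simulation 2.20 and 1.03)
- Adjusting for team type: 0.400 / (0.8 × 0.25 + 0.2 × 0.16) = 0.400 / 0.232 = 1.72 (simulation about 1.7)
- RAT-only: 2.0

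So the bias can go either way, and a team-type covariate alone does not restore the true slope.

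**3. Cost of restriction.** Assume 166 teams, an even exposure split, a true difference of 2 percentage points, SD 4 and two-sided alpha 0.05. Power without misassignment is 0.896.

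| f | Pooled, k = 0 | RAT-only |
|---|---|---|
| 5% | 0.864 | 0.881 |
| 10% | 0.826 | 0.863 |
| 20% | 0.731 | 0.821 |
| 30% | 0.616 | 0.769 |

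At k = 0.5 the two are nearly level. For f = 10% the pooled factor is 0.95, which gives 0.864 against 0.863; for f = 20% it is 0.90, which gives 0.826 against 0.821. Above half agreement, restriction loses power. For the same exposure split, RAT-only intervals are wider by 1/√(1 − f): 1/√0.9 = 1.05 at f = 10% and 1/√0.8 = 1.12 at f = 20%.

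**The case against.** The strongest objection is that the document never says where screening takes place, that N-RAT patients are admitted elsewhere first, or how the registry's patient-centred percentage treats a patient seen by two teams. The premise rests on a label and a timing indicator. That indicator is the percentage of patients meeting a target in team-centred results; it is not the Q9 exposure and does not show which team did the screen. This stands as a limit: the point is that exposure may be misassigned, not that it is.

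A reader might infer that both early steps normally happen at the admitting team, so that Hypotheses 1 and 2 are alike diluted in favour of the null. The document does not support that. For Hypothesis 2, a 72-hour window leaves room for a first specialist assessment after transfer, and Q20 asks about a bedside assessment without specifying the first one. Shrinkage proportional to the N-RAT share also needs an equal exposure mix and no agreement between teams. The rule for one survey covering two teams expects some agreement, and a differing mix can push the slope upward.

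A reader might also infer that RAT-only should become the primary analysis. That trade-off is debatable: at half agreement it gains nothing in power. The survey closed in October 2020 and the plan cites a source accessed on 29.12.2020, so the primary population would be narrowed after the survey data were collected.

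Finally, the sensitivity examples are an open list, so a RAT-only run is not excluded. It is not specified either, and that is the gap.

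**Conclusion.** The concern holds in a limited form. The plan uses N-RATs' own answers as exposure against pneumonia counted from clock start, and nothing in the regressions or the named sensitivity analyses deals with team type. For Hypothesis 1, misassigned exposure in N-RAT rows is a fair inference from the 4-hour indicator and the team label. For Hypothesis 2 it is possible but less clear.

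The size cannot be settled from the document. It ranges from no shrinkage under full agreement to shrinkage equal to the N-RAT share under none, and with unequal mix and baseline incidence the bias can have either sign. All of this rests on an assumed share, an assumed level of agreement and an attribution rule that the plan does not state. It is a low-cost improvement to the plan and does not invalidate the all-team analysis.

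**What to change.** In *Statistical analyses*, the Q9 and Q20 rows of Table 1, and *Sensitivity analysis*:

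- Prespecify a RAT-only regression for Hypothesis 1, and the same for Hypothesis 2, using the Hospital Team variable already recorded. Report each beside the all-team regression, with the number of teams of each type.
- State how a patient treated by two teams is attributed in the pneumonia percentage, and use one description of the 7-day window (clock start or admission) throughout.
- State that a null all-team result for Hypothesis 1 will not be interpreted as no difference without the RAT-only result.
- Do not rely on a team-type covariate alone, since it leaves the misassigned exposure in place.

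The cost is plan wording and one filter on a coded variable. The RAT-only estimates will rest on fewer teams and have wider intervals, about 5% wider at a 10% N-RAT share and 12% at 20%. The all-team result is kept.
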